#### Prior/Concomitant Medication

Incomplete prior/concomitant medication dates will be imputed as follows:

- If the medication date is missing completely, then the medication date will be replaced by the start date of the first study intervention.
- If the day of medication date is missing, but the month and year are equal to the start date of
  the first study intervention, then the medication date will be replaced by the start date of the
  first study intervention. For example, if the medication start date is --/JAN/2015, and study
  intervention start date is 15/JAN/2015, then the imputed medication start date will be
  15/JAN2015.
- If both the day and month of medication start date are missing but the start year is equal to the start date of the first study intervention, then the medication date will be replaced by the start date of the first study intervention. For example, if the medication start date is --/---/2014, and study intervention start date is 19/NOV/2014, then the imputed medication start date will be 19/NOV/2014.
- In all other cases, the missing medication day or month will be replaced by 1.
- In the case that the imputed start date occurs after the medication end date, the medication end date will be used as the start date.

- Incomplete end date will be replaced by the last day of the month (if day is missing only), if not
  resulting in a date later than the date of subject's death. In the latter case, the date of death will
  be used to impute the incomplete end date.
- In all other cases, the incomplete medication end date will not be imputed.

#### Subsequent Anti-Cancer Therapy

Incomplete dates for start date of subsequent anti-cancer therapy (drug therapy, radiation, surgery) will be imputed as follows and will be used for determining censoring dates for efficacy analyses and in the derivation of the end of on-treatment period.

If only day is missing, it will be imputed as the last day of the month unless the end date of subsequent anti-cancer therapy is before that date. In that case, the incomplete anti-cancer therapy start date will be imputed as the end date of the anti-cancer therapy. If both day and month are missing, no imputation will be performed, and the date of subsequent anti-cancer therapy will not be used for any calculations.

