Dipstick Urinalysis	х	x		x			Perform at Visit 6 (Week 8) and then Q8W	x				Full urinalysis (dipstick + microscopic analysis) should be performed only at Screening and EoT. If dipstick urinalysis at other assessments is abnormal, full analysis should be performed. See Appendix 6.
Free T4, TSH	X	X				Х	Q6W		X			

		Treat	ment l	Perio	d: M3	3814+	avelumab	End	of Trea	tment	(EoT)/FU	Notes
Study Period	Screening	DL	T Peri	od				EoT	EoT Safety FU		Long-term FU	
Visit	-1	1	2	3	4	5	n				Q12W	During on-treatment period, after Day 29, visits
								(Within				will be every 2 wks on days of avelumab infusions until EoT.
Study Day (± Visit window)	-28 to -1	1	15 (± 1)	22 (± 1)	29 (± 1)		n + 14 d (± 2)	7 days of		90 d (± 5)	(± 7)	All participants discontinuing study interventions for any reason must undergo EoT Visit within 7 days after decision to discontinue study interventions, but (if possible) before any new antineoplastic therapy is started.
								nue)				The safety follow-up period will be 30 days (± 5 days) and 90 days (± 5 days) after the last dose of avelumab, see Section 4.1.1.3.
M3814		Cont	inuou	s BID	dosi	ing (7	days/wk)					See Section 6.6.5.1 for details.
Premedication (avelumab)		x	x		x	X						Required only for first 4 avelumab infusions, as needed thereafter. See Section 6.5.5.
Avelumab		x	x		x	x	x					800 mg iv Q2W until PD. For post-PD treatment, see Section 6.6.6. For post-CR treatment, see Section 4.1.1.2.
12-Lead ECG (including QTcF)	х	x	x	x				x				PK-matched digital 12-lead resting ECG will be performed in triplicate at predose,1, 2 and 6 h post-M3814 administration before blood collection for PK, CCI sampling, followed by vital signs after the morning dose only. The assessment should be performed after the participant has been in supine position breathing quietly for ≥ 5 min at predose and all postdose sampling times.
Tumor Assessment (RECIST v 1.1)	х						Day 56, Day 112, Day 168, then Q12W	x	x		x	Tumor imaging by CT or MRI at Baseline to document tumor lesion burden. Can be up to 28 days prior to first study intervention. Then at D56, D112, D168 and then Q12W, until confirmed PD, the start of subsequent systemic anticancer therapy, or the end of the study. At EoT/Long-term FU, tumor response assessment is only required if participant has not progressed or has not started a new treatment.

		Treat	ment l	Perio	d: M3	814+	avelumab	End	of Trea	tment	(EoT)/FU	Notes
Study Period	Screening	DL	T Peri	od				EoT	Safet	Safety FU Long-term FU		

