6.5.4 Other Interventions

Surgery to any tumor lesion for symptom management or tumor control is permitted during the study intervention according to rules defined in Section 6.6.7. For any other surgical interventions planned during the study, study intervention should be delayed for up to a maximum of 4 weeks to allow participant's recovery.

Palliative short course, limited field (i.e. \leq 10 fractions and \leq 30% bone marrow involvement or per institutional standard) RT may be administered at any time after the end of the DLT period in Part A and Part B, and after the FE Assessment Period in Part FE. However, dosing of M3814 must be suspended \geq 24 hours prior to start of RT and must not be resumed until \geq 24 hours after the last RT dose. The assessment of PD will be made according to RECIST v 1.1 and not based on the necessity for palliative RT.

Radiotherapy (Part A, Part B, and Part FE) is not permitted, with the exception of palliative RT as described above.

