### Definition of on-treatment period

The on-treatment period is defined as the time from the first dose of study treatment through the minimum of (last date of study intervention + 30 days, start day of new anti-cancer drug therapy - 1 day, death).

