#### Objective Response

The confirmed objective response rate (ORR) is defined as the proportion of subjects having reached a confirmed BOR of CR or PR according to RECIST v1.1, as evaluated by the Investigator. Subjects with BOR of non-CR/non-PD are not considered to have achieved objective response. Subjects who do not have a post-baseline radiographic tumor assessment due to early progression; who receive anti-cancer treatments other than the study intervention prior to reaching a CR or PR; or who die, progress, or drop out for any reason prior to reaching a CR or PR will be counted as non-responders in the assessment of ORR.

ORR will be tabulated by cohort dose level along with the two-sided 95% CI using the Clopper-Pearson method (exact CI for a binomial proportion as computed by default by the SAS FREQ procedure using the EXACT option).

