#### 15.1 Adverse Events

Analysis set: SAF

The severity of AEs will be graded using the National Cancer Institute – Common Terminology Criteria for Adverse Events (NCI-CTCAE) v5. If a particular AE's severity is not specifically graded by this guidance, the Investigator uses the general NCI-CTCAE definitions of Grade 1 through Grade 5 following his or her best medical judgment. The latest MedDRA version at the time of data cut-off will be used to code AEs according to SOC and PT.

- Treatment Emergent Adverse Events (TEAEs) are events with onset dates occurring during the on-treatment period, or those that worsen in severity during the on-treatment period. All analyses will be based on TEAEs unless otherwise specified.
- Related Adverse Events have a relationship to study treatment of "Related", or missing relatedness, as reported by the Investigator on the "Adverse Events Details" eCRF page. Relatedness is defined separately for each study intervention component.
- Serious Adverse Events (SAEs) are those recorded on the "Adverse Events Details" eCRF
  page as Serious Adverse Event = "Yes".
- Adverse Events Leading to Treatment Discontinuation are those recorded on the "Adverse Events Details" eCRF page as Action(s) taken with M3814/ avelumab/ radiotherapy = "Drug withdrawn".
- Adverse Events Leading to Death are those recorded on the "Adverse Events Details" eCRF page as Outcome = "Fatal" as well as AEs of Grade 5.
- Adverse Events of Special Interest (AESIs) for this study include infusion related reactions (IRRs) / hypersensitivities and immune-related AEs (irAEs) / autoimmune disorders. IRRs and irAEs are identified based on a list of MedDRA PTs and other qualifying criteria, as specified in Appendix I.

Details on the handling of incomplete AE-related dates are specified in Section 9.4.

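### The SAP gives two conflicting rules for when the on-treatment (TEAE) period ends, and does not say which anti-cancer therapies stop efficacy follow-up

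*SAP*

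**What the plan says.** **On-treatment period.** SAP Section 9.1 takes the earliest of the last study intervention plus 30 days and "start day of new anti-cancer drug therapy - 1 day, death". Only drug therapy is named. SAP Section 9.3 (Handling of Missing Data, paragraph on subsequent anti-cancer therapy) begins: "Incomplete dates for start date of subsequent anti-cancer therapy (drug therapy, radiation, surgery) will be imputed as follows and will be used for determining censoring". In full, these dates are "used for determining censoring dates for efficacy analyses and in the derivation of the end of on-treatment period".

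**What depends on it.** SAP Section 15.1 defines TEAEs as "events with onset dates occurring during the on-treatment period" or as worsening in that period, and makes TEAEs the default for AE analyses. Worst laboratory grades, liver-function categories, vital-sign changes and ECG abnormalities use the same period.

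**Efficacy rules.** SAP Section 14.1 closes the BOR window at subsequent, further or new therapy, using all three words. For ORR it counts as non-responders those "who receive anti-cancer treatments other than the study intervention prior to reaching a CR or PR". Tables 7 and 8 in Section 14.4 censor PFS and DOR at new anti-cancer therapy. None of these lists therapy types.

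**Protocol.** Section 9.4.2 runs TEAEs from first dose to 30 days after the last dose, with no cut for other therapy. Section 9.4.1 has no stop at other therapy for BOR or PFS. Section 6.5.4 permits limited palliative RT after the DLT or food-effect period, with M3814 paused around it, and adds: "The assessment of PD will be made according to RECIST v 1.1 and not based on the necessity for palliative RT". Section 6.5.4 also permits tumor surgery, under the rules of Section 6.6.7.

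**The concern.** One derived variable, the on-treatment end date, has two definitions in the same SAP. Whichever is programmed decides which adverse events and laboratory results reach the main safety tables.

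The undefined efficacy terms raise a related problem. Palliative RT during study treatment is foreseeable, because the protocol provides for it and for resuming M3814 afterwards. Such a participant could be followed for PFS or censored, and could be a responder or a fixed non-responder, depending on how an analyst reads an undefined term. In dose levels of 3 to 6, settling this after the data are seen would be a post hoc choice with visible effect.

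SAP Section 7 states that the protocol's methods were adopted and lists only PK changes. The TEAE cut, the censoring rule and the non-responder rule are therefore undeclared additions to the protocol.

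**Working it through.** The plan states no figure on this point, so there is none to reproduce. The check applies each reading to the same cases. Dates and counts are assumptions unless a source is given.

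**1. On-treatment end.** Let L be the study day of the last dose.
- Drug only (SAP 9.1; same as the protocol window when no new drug is started): end = L + 30.
- Radiation or surgery counted (SAP 9.3), starting on Day r: end = min(L + 30, r − 1).

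*Therapy after the last dose*, r = L + k: days lost = 30 − (k − 1).
- k = 1: 30 days
- k = 10: 21 days
- k = 20: 11 days

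*Palliative RT during treatment, if treated as subsequent therapy*:

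| RT day | Last dose | End, drug only | End, RT counted | Days lost |
|---|---|---|---|---|
| 60 | 168 | 198 | 59 | 139 |
| 22 | 84 | 114 | 21 | 93 |
| 22 | 168 | 198 | 21 | 177 |
| 22 | 351 | 381 | 21 | 360 |

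Day 22 is the first day after the 21-day DLT period in Part A. In the first row, 168 − 60 + 1 = 109 of the 139 days fall on or before the last dose, and the other 30 are follow-up.

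**2. ORR.** Take one responder whose palliative RT preceded the PR. Dose-level size is 3 to 6 (protocol Section 6.6.4); intervals are Clopper-Pearson 95% (SAP Section 14.1).
- n = 6: 1/6 = 16.7% (0.4 to 64.1) if counted; 0/6 = 0% (0 to 45.9) if not.
- n = 3: 1/3 = 33.3% (0.8 to 90.6) if counted; 0/3 = 0% (0 to 70.8) if not.

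**3. PFS, illustration only.** Months = study day / 30.4375. With no PD at Day 56, RT on Day 60 and PD at Day 112, the result is an event at 112/30.4375 = 3.68 months, or censoring at 56/30.4375 = 1.84 months (Table 7 goes back to the last evaluable scan).

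Six assumed participants have PD at Days 56, 56, 112, 112, 168 and 252.
- None censored: S(112) = 4/6 × 2/4 = 0.333; median 3.68 months.
- One Day 112 case censored at Day 56: S(112) = 4/6 × 2/3 = 0.444; median still 3.68 months.
- Both censored at Day 56: S stays at 0.667 until Day 168, then 0.667 × 1/2 = 0.333; median 5.52 months.

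A simulation assumed exponential PFS with median 3.0 months and RT in 10%, 20% or 30% of participants, on average one month before PD. Censoring at the last scheduled scan moved the median to 3.1, 3.3 or 3.6 months; censoring at the RT date gave 3.2, 3.5 or 3.8. In a variant with RT timing unrelated to progression and censoring at the RT date, there was no shift.

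**4. Surgery.** Protocol Section 6.6.7 requires RECIST progression to be documented before the procedure. The PFS/DOR event is then already dated and the BOR window closed. Only the on-treatment end date can change.

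**The case against.** The strongest reply is that SAP terminology already excludes on-treatment RT. Section 9.3 concerns subsequent therapy. Section 12.2, under that title, draws drugs, radiotherapy and surgery from eCRF pages for treatment after discontinuation. The date-of-last-contact rule uses similar wording, and concomitant procedures have their own page. This is plausible, and it would limit the TEAE loss to 30 days. It does not remove the conflict between Sections 9.1 and 9.3 for radiation or surgery after the last dose. Nor does it reach the ORR rule, which covers any treatment other than the study intervention.

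The ORR rule can also be defended as conservative, since it avoids crediting local RT to the study drugs. That is a fair choice, but it should be stated and declared.

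Three stronger readings are tempting, and the documents do not support them:
- **That the SAP contradicts a single systemic-only protocol definition.** The Schedule of Activities does continue scans "until confirmed PD, the start of subsequent systemic anticancer therapy, or the end of the study". But protocol Sections 6.5.3, 8.1.1.1 and 8.1.1.2 refer to new anticancer treatment, new cancer therapy or a new treatment, without that limit. The direct contradiction is inside the SAP.
- **That permitted surgery can change ORR, PFS or DOR.** Step 4 shows that it cannot.
- **That PFS is biased upward by a known amount.** The RT frequency and timing are assumed, and one censored case in six left the median unchanged.

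**Conclusion.** The concern holds in a limited form. SAP Sections 9.1 and 9.3 give incompatible rules for the on-treatment end, and so for TEAEs. Counting radiation or surgery costs up to 30 days of protocol-defined TEAE follow-up when it comes after the last dose. It costs more (139 of 198 days in the assumed case) only if permitted on-treatment RT is read as subsequent therapy, which the SAP neither says nor rules out.

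The BOR, ORR and PFS/DOR rules leave the therapy type open. Read literally, the ORR rule overrides a confirmed PR that follows permitted palliative RT: 16.7 points in a dose level of 6, 33.3 in one of 3. Any PFS shift is illustrative.

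The correction should be made before database lock, but it is not critical. The affected endpoints are secondary and descriptive, and no hypothesis is tested. The DLT endpoint is untouched, because palliative RT is allowed only after the DLT period.

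**What to change.** 1. In SAP Section 9.3, let only drug-therapy dates feed the end of the on-treatment period, to match Section 9.1.
2. In SAP Sections 14.1, 14.2 and 14.4, including Tables 7 and 8, use one pre-specified term for the therapy that stops efficacy follow-up, naming the types and the timing (on treatment or after discontinuation). State that palliative RT permitted by protocol Section 6.5.4 while study treatment continues is neither subsequent nor new therapy, and does not by itself make a participant a non-responder.
3. In SAP Section 7, list the TEAE cut, the censoring rule and the non-responder rule as additions to protocol Sections 9.4.1 and 9.4.2.

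I would not add a rule making irradiated target lesions not evaluable. If the time-point response then became NE, Section 14.4 would not count the scan as adequate, and its limits of 16 or 24 weeks since the last assessment could bring the censoring back.

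The cost is SAP wording only; drug, radiotherapy and surgery details already have eCRF pages. The downside is that some efficacy follow-up will include time after local palliative RT.

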#### Exposure

For each treatment component, in case the last administration date is incomplete, the date of last administration of study intervention will be taken from the "Treatment Termination" eCRF pages.

#### Date of Last Contact

The last alive date will be derived for subjects not known to have died at the analysis cut-off using the latest complete date among the following:

- All subject assessment dates (blood draws (laboratory, PK), vital signs, performance status, ECG, tumor assessments)
- Start and end dates of anti-cancer therapies administered after study treatment discontinuation
- AE start and end dates
- Date last known to be alive collected on the eCRF page "Subject Status / Survival Followup"
- Study intervention start and end dates
- Date of discontinuation from the "Study Termination" eCRF page (not used if reason for discontinuation is lost to follow-up)

Only dates associated with actual examinations of the subject will be used in the derivation. Dates associated with a technical operation unrelated to subject status such as the date a blood sample was processed will not be used.

#### Death date

Missing or partial death dates will be imputed based on the last contact date:

- If the date is missing it will be imputed as day after date of last contact from the eCRF
  "Subject Status / Survival Follow-up" page
- If the day or both day and month are missing, death will be imputed to the maximum of the full (non-imputed) day after the date of last contact and the following:
  - Missing day: 1st day of the month and year of death
  - Missing day and month: January 1st of the year of death

If the day is missing from the date of last contact, it will be imputed to 1st day of the month and year of last contact only if derived from the survival page.

#### Tumor assessments

All investigation dates (e.g., X-ray, CT scan) must be completed with day, month and year.

If there are multiple scan dates associated with an evaluation, i.e., radiological assessments occur over a series of days rather the same day, the choice of date of assessment could impact the date of progression and/or date of response. If there are multiple scan dates associated with an evaluation, the earliest of the scan dates associated with the evaluation will be used as the date of assessment.

If one or more investigation dates for an evaluation are incomplete but other investigation dates are available, the incomplete date(s) are not considered for calculation of the assessment date and assessment date is calculated as the earliest of all investigation dates (e.g., X-ray, CT-scan).

If all measurement dates for an evaluation have no day recorded, the 1st of the month is used.

If the month is not completed, for any of the investigations for an evaluation, the respective assessment will be considered to be at the date which is exactly between the previous and the following assessment. If both a previous and following assessments are not available, this assessment will not be used for any calculations.

### 10 Study Participants

## 10.1 Disposition of Participants and Discontinuations

Analysis set: Screening

The following information will be summarized by dose level and overall within each study part:

- Number of participants screened
- Number of participants who discontinued the study prior to study intervention, and by reason (e.g., subject did not meet all eligibility criteria, withdrew informed consent, died prior to receiving treatment)
- Number of participants who received at least one dose of any study intervention
- Number and percentage of participants with at least one study intervention ongoing
- Number and percentage of participants who received at least one dose of study intervention, displayed by specific study intervention component
- Number and percentage of participants with study intervention ongoing, displayed by specific study intervention component
- Number and percentage of participants who discontinued study intervention, overall and by reason, displayed by specific study intervention component
- Number and percentage of participants who discontinued all study intervention, overall and by main reason (reason for discontinuation of last study intervention)
- Number and percentage of participants who re-initiated study intervention
- Number and percentage of participants who discontinued study intervention after reinitiation, overall and by primary reason, displayed by specific study intervention component
- Number and percentage of participants who received subsequent anti-cancer therapy
- Number of participants who discontinued the study and main reason

The number and percentage of participants in each of the above disposition categories will be presented by assigned study intervention group and overall. Percentages will be presented with respect to the number of SAF Analysis Set participants.

The number of participants in the analysis populations outlined in Section 8.2 will be summarized by study intervention group and by site.

The number and percentage of participants enrolled by region and by country within region will be summarized.

All relevant participant disposition data will be presented in data listings.

### 10.2 COVID-19 Impact

No changes to the per-protocol planned analyses of safety or efficacy endpoints will be made due to the impact of coronavirus disease 2019 (COVID-19) outbreak.

CONFIDENTIAL

Additional outputs (summary table and listing) will be generated in order to describe and quantify the impact of COVID-19 pandemic on the following parameters:

- Subjects potentially affected by COVID-19
- Adverse Events
- Protocol deviations (important and non-important)
- Missed Visits
- Missed efficacy evaluations
- Tele-Visits performed
- Drug Administration: missed doses
- Drug Administration: dose delays
- Treatment Discontinuation
- Study Discontinuation
- Death

Potentially affected subjects are defined as:

- a) Patients who started treatment after start of the COVID-19 pandemic, or
- b) Patients who started treatment prior to start of the COVID-19 pandemic and are still ongoing after the start of the pandemic.

The start of COVID-19 pandemic will be defined by country as the earliest date of either: (1) the date of the first death attributed to COVID-19 in the patient's country, according to the published data by European Centre for Disease Prevention and Control on 26th June 2020 or (2) 11th March 2020 (when the WHO declared COVID-19 pandemic).

A frequency table will be produced for the SAF analysis set to present the number of subjects with any of the above-listed study events attributable to COVID-19.

Additional COVID-19-related outputs will also be produced for protocol deviations, adverse events, and exposure. Please refer to those sections of this document for further details.

